8.1. Immunogenicity assessments

Biological samples will be used for research planned in the protocol and for purposes related to the improvement, development and quality assurance of the laboratory tests described in this protocol.

Findings in this or future studies may make it desirable to use samples acquired in this study for research not planned in this protocol. In this case, all participants in countries where this is allowed will be asked to give consent to allow GSK or a contracted partner, to use the samples for further research. The further research will be subject to prior Independent Ethics Committee (IEC)/ Institutional Review Board (IRB) approval, if required by local legislation.

Information on further research and its rationale can be obtained from GSK.

Sample testing will be done in accordance with the recorded consent of the individual participant's parent(s)/LAR(s).

By default, collected samples will be stored for a maximum of 20 years. This storage period begins when the last participant performs the last study visit. This timeline can be adapted based on local laws, regulations or guidelines requiring different timeframes or procedures. In all cases, the storage period should be aligned with participant's consent. These additional requirements must be formally communicated to, discussed and agreed with GSK.

8.1.1. Biological samples

Per participant, an overall volume of at least 6 mL (not more than 7.5 mL) will be collected during the entire study period. Refer to [Table 8](#) and SoA (Section 1.3) for details of volumes collected for different assessments.

Table 8 Biological samples

Group	Sample type	Quantity	Unit	Timepoint
Co-administration	Blood*	At least 2**	mL	Visit 2 (Month 0.5)
				Visit 6 (Month 2.5)
				Visit 7 (Month 3.5)
Staggered group	Blood*	At least 2**	mL	Visit 1 (Day 1)
				Visit 5 (Month 2)
				Visit 7 (Month 3.5)

mL: milliliter

*Blood sampling to be done before study intervention administration.

**Volume of the blood sample should be between 2 and 2.5 mL.

8.1.2. Laboratory assays

Table 9 Laboratory assays

Test Classification	System	Component	Method	Laboratory*
Humoral Immunity (Antibody determination)	Serum	Rotavirus Ab, IgA	ELISA	GSK designated lab in China
		IPV Ab, type 1 IPV Ab, type 2 IPV Ab, type 3	Microneutralization assay	GSK designated lab in China

Ab: Antibody; IgA: Immunoglobulin A; IPV: Inactivated poliovirus vaccine; ELISA: Enzyme Linked Immunosorbent Assay

*Refer to the list of clinical laboratories for details.

Please refer to Section 10.2 for a brief description of the assays performed in the study.

The addresses of clinical laboratories used for sample analysis are provided in a separate document accompanying this study protocol.

8.1.3. Immunological read-outs

Table 10 Immunological read-outs

Blood sampling timepoint		Subset name	No. participants	Component
Type of contact and timepoint	Sampling timepoint			
Visit 1 (Day 1)	Pre-first Dose administration	Staggered group	200	Rotavirus Ab, IgA IPV Ab, type 1 IPV Ab, type 2 IPV Ab, type 3
Visit 2 (Month 0.5)	Pre-first Dose administration	Co-administration group	200	Rotavirus Ab, IgA IPV Ab, type 1 IPV Ab, type 2 IPV Ab, type 3
Visit 5 (Month 2)	Post Dose 2 of Rotarix PCV-free	Staggered group	200	Rotavirus Ab, IgA
Visit 6 (Month 2.5)	Post Dose 2 of Rotarix PCV-free	Co-administration group	200	Rotavirus Ab, IgA
Visit 7 (Month 3.5)	Post Dose 3 of IPV	All participants (Co-administration group + Staggered group)	400	IPV Ab, type 1 IPV Ab, type 2 IPV Ab, type 3

Ab: Antibody; IgA: Immunoglobulin A; IPV: Inactivated poliovirus vaccine; PCV: *Porcine circovirus*; PCV-free: no detection of PCV-1 and PCV-2 according to the limit of detection of the tests used.

8.1.4. Immunological correlates of protection

No recognized immunological correlate of protection (CoP) has been established for the antigen used as part of the HRV vaccine. However, an analysis by Cheuvart et al. in 2014 showed that post-vaccination anti-RV IgA seropositivity (Ab concentration ≥ 20 U/mL, measured by ELISA) is a correlate of vaccine efficacy in clinical trials of *Rotarix* [Cheuvart, 2014]. This was confirmed by an independent research group in 2020 [Baker, 2020].

Antibodies against poliovirus types 1, 2 and 3 will be determined by a virus microneutralization test adapted from the WHO Guidelines for WHO/EPI Collaborative Studies on Poliomyelitis [WHO position paper, 1993]. Titers will be expressed in terms of the reciprocal of the dilution resulting in 50% inhibition. The lowest dilution at which serum samples will be tested is 1:8. Antibody titers greater than or equal to 1:8 will be considered as protective.

The immunological assay results will be communicated to the investigator after the end of the study.

8.2. Safety assessments

The investigator(s) and their designees are responsible for detecting, documenting, and reporting events that meet the definition of an AE or SAE. The investigator and designees are responsible for following up AEs that are serious, or that caused the participant's withdrawal from the study interventions or study.

Note: Details of COVID-19 infection-related signs and symptoms will be recorded in a separate eCRF page.

8.2.1. Pre-intervention administration procedures

8.2.1.1. Collection of demographic data

Record demographic data such as date of birth including gestational age, gender, race and ethnicity in the participants' eCRF.

Collection of race and ethnicity data is necessary to meet the inclusion criteria of the study participants, and to determine if the study participants are truly representative of the impacted population.

8.2.1.2. Medical/vaccination history

Obtain the participant's medical/vaccination history by interviewing the parent(s)/LAR(s) and/or review of the participant's medical records. Record any pre-existing conditions, signs and/or symptoms present prior to the first dose of study intervention administration in the eCRF.

8.2.1.3. Physical examination

- Axillary body temperature* of each participant needs to be measured prior to any study intervention administration and recorded in the eCRF. If the participant has fever (defined as temperature $\geq 37.5^{\circ}\text{C}$) on the day of administration of the study intervention, the study visit will be rescheduled within the allowed interval for this visit (see [Table 3](#) and [Table 4](#)).

*Axilla is the preferred route to measure temperature in China. If temperature is taken by other routes, conversion can be made as per local guidelines:

- Axillary temperature = oral temperature - 0.2°C ;
- Axillary temperature = rectal temperature - 0.3°C .

- Weight and height must be collected at Visit 1 and recorded in the eCRF.
- Physical examination at each study visit subsequent to the first study intervention administration visit will be performed only if the participant's parent(s)/LAR(s) indicates during questioning that there might be some underlying pathology(ies) or if deemed necessary by the investigator or delegate.
- If the investigator determines that the participant's health on the day of study intervention administration temporarily precludes dosing, the visit will be rescheduled.
- Treatment of any abnormality observed during this examination has to be performed according to local medical practice outside this study or by referral to an appropriate health care provider.

8.2.1.4. Warnings and precautions to administration of study interventions

Warnings and precautions to administration of study intervention must be checked at each visit with planned administration of study intervention as specified in SoA (Section 1.3).

Refer to the approved product label/package insert.

8.3. Adverse Events (AEs), Serious Adverse Events (SAEs) and other safety reporting**8.3.1. Time period and frequency for collecting AE, SAE and other safety information**

An overview of the protocol required reporting periods for safety information and for AEs/SAEs leading to withdrawal is given in [Table 11](#) and [Table 12](#).

The investigator or designee will record and immediately report all SAEs in enrolled participants to the sponsor or designee via the Expedited AE Reporting Form. Reporting should, under no circumstances, occur later than 24 hours after the investigator becomes aware of an SAE, as indicated in Section 10.3.8. The investigator will submit any updated SAE data to the sponsor within 24 hours of it being available.

A post-study AE/SAE is defined as any event that occurs outside of the AE/SAE reporting periods defined in [Table 11](#). Investigators are not obligated to actively seek AEs or SAEs from former study participants. However, if the investigator learns of any SAE, including a death, at any time after a participant has been discharged from the study, and if the investigator considers the event to be reasonably related to the study intervention, the investigator will promptly notify the study contact for reporting SAEs mentioned in the [Table 13](#).

Table 11 Timeframes for collecting and reporting of safety information

Event	V1 ⁺ D1	V2 ⁺ M0.5	V3 ⁺ M1	V4 ⁺ M1.5	V5 ⁺ M2	V6 ⁺ M2.5	V7 ⁺ (Study Conclusion) M 3.5
Solicited events Co-ad group							
Solicited events Staggered group							
Unsolicited AEs Co-ad group*							
Unsolicited AEs Staggered group*							
AEs that led to withdrawal from the study							
SAEs							
SAEs related to study participation** or concurrent GSK medication/ vaccine							

AE: Adverse Event; Co-ad: Co-administration group; V: Visit; D: Day, M: Month; SAE: Serious Adverse Event

* Unsolicited AEs will be collected only post *Rotarix* administration.

** Any SAEs assessed as related to study participation (e.g., protocol-mandated procedures, invasive tests, or change in existing therapy) or related to a GSK product will be recorded from the time a participant's parent(s)/LAR consents to participate in the study.

† Refer to [Table 3](#) (for Co-administration group) and [Table 4](#) (for Staggered group) for information about optimal interval.

8.3.2. Method of detecting AEs and SAEs

Detection and recording of AE/SAE are detailed in Section [10.3.6.1](#).Assessment of AE/SAE intensity, causality and outcome are described in Section [10.3.7](#).

Care will be taken not to introduce bias when detecting AEs and SAEs. Open-ended and non-leading verbal questioning of participants' parent(s)/LAR(s) is the preferred method of acquiring information related to an AE/SAE.

8.3.3. Regulatory reporting requirements for SAEs

Once an investigator (or designee) becomes aware that a study participant has experienced an SAE, it must be reported to GSK using the required documentation and within the timeframes mentioned in [Table 12](#). This is essential for GSK to meet legal obligations and ethical responsibilities for participant safety and the safety of a study intervention under clinical investigation.

For SAEs, the investigator must always provide an assessment of causality at the time of the initial report, as defined in the Section [10.3.7.2](#).

Local regulatory requirements and sponsor policy for preparation of an investigator safety report of Suspected Unexpected Serious Adverse Reaction (SUSAR) must be followed. These reports will be forwarded to investigators as necessary.

The sponsor has the legal responsibility to notify local authorities/regulatory agencies about the safety of an investigational study intervention. The sponsor will comply with country-specific regulatory requirements related to safety reporting to the regulatory authority, IRB/IEC and investigators.

Please refer to Section [10.3.8](#) for further details regarding the reporting of SAEs.

Table 12 Timeframes for submitting SAE and other events reports to GSK

Type of event	Initial reports		Follow-up of relevant information on a previous report	
	Timeframe	Documents	Timeframe	Documents
SAEs	24 hours*†‡	paper/electronic Expedited Adverse Events Report	24 hours*	paper/electronic Expedited Adverse Events Report

* Timeframe allowed after receipt or awareness of the information by the investigator/site staff.

† Paper Expedited Adverse Events Report will be dated and signed by the investigator (or designee).

‡ For each SAE, the investigator(s) must document in the medical notes that they have reviewed the SAE and have provided an assessment of causality.

8.3.4. Treatment of expedited adverse events (SAE)

Any medication administered for the treatment of an SAE should be recorded in the Expedited AE Report of the participant's eCRF screen (refer to Section 10.3.8.1).

8.3.5. Participant card

The investigator (or designee) must provide the participant's parent(s)/LAR(s) with a "participant card" containing information about the clinical study. The participant's parent(s)/LAR(s) must be instructed to always keep the participant card in their possession for the duration of the study. In an emergency, this card serves to inform the responsible attending physician/LAR/caregiver/family member that the participant is in a clinical study and that relevant information may be obtained by contacting the investigator(s) or their back up.

8.3.6. Medical device deficiencies

Both study groups have study interventions that are a combination product constituted of a device **CCI** [REDACTED] and biologic product. Refer to the [Glossary of terms](#) for the definition of combination product and medical device deficiency.

8.3.6.1. Detection, follow-up, and prompt reporting of medical device deficiency

The investigator is responsible for the detection, documentation and prompt reporting of any medical device deficiency occurring during the study to GSK. This applies to any medical device provided for the conduct of the study.

Device deficiencies will be reported to GSK within 24 hours after the investigator determines that the event meets the protocol definition of a device deficiency. Refer to Section 10.6 for definitions and details on recording and reporting of these events.

The investigator will ensure that follow-up includes any additional investigations to elucidate the nature and/or relatedness of the device deficiency to the incident.

New or updated information will be recorded on the originally completed form with all changes signed and dated by the investigator and reported to GSK within 24 hours.

Medical device deficiencies and any associated AE/SAEs for associated person (i.e., spouse, caregiver, site staff) will also be collected. The associated person will be provided with a safety reporting information and authorization letter.

Follow-up applies to all participants, including those who discontinue study intervention or the study, and associated persons.

8.3.6.2. Regulatory reporting of medical device deficiency when used as combination product

The investigator will promptly report all device deficiencies occurring with any medical device provided for use in the study to GSK. GSK has a legal responsibility to notify appropriate regulatory authorities and other entities about safety information linked to medical devices being used in clinical studies. Refer to Section [10.6.3](#) for details of reporting.

The investigator, or responsible person according to local requirements (e.g., the head of the medical institution), will comply with the applicable local regulatory requirements linked to the reporting of device deficiencies to the IRB/IEC.

8.4. Pharmacokinetics

This section is not applicable.

8.5. Genetics

This section is not applicable.

8.6. Biomarkers

This section is not applicable.

8.7. Immunogenicity assessments

Immunogenicity is described in Section [8.1](#).

8.8. Health outcomes

This section is not applicable.

9. STATISTICAL CONSIDERATIONS

9.1. Statistical hypotheses

The study includes 1 confirmatory objective. The non-inferiority margin associated with the objective is provided in [Table 14](#).

Table 14 Study objective and null hypothesis

Primary objective	Null hypothesis

 To demonstrate the immunological non-inferiority of IPV when co-administered with Rotarix PCV-free compared with IPV administered alone. 	
 The difference in seroconversion rate between the Co-administration group and (minus) the Staggered group is below -10% for at least 1 of the anti-poliovirus types 1, 2 and 3 Abs.

Ab: Antibody; IPV: Inactivated poliovirus vaccine; PCV: *Porcine circovirus*

The global type I error will be 2.5%. The primary objective will be achieved if the lower limit of the 2-sided 95% CI for the group difference (Co-administration group minus Staggered group) in seroconversion rate is greater than or equal to -10% for each of the anti-poliovirus types 1, 2 and 3 antibodies.

9.2. Analysis sets

Table 15 Analysis sets

Analysis set	Description
Screened	All participants who were screened for eligibility.
Enrolled Set	
 All participants who entered the study (who were randomized or received study intervention or underwent a post-screening study procedure). Note: screening failures (who never passed screening even if rescreened) and participants screened but never enrolled into the study (Met eligibility but not needed) are excluded from the Enrolled Set as they did not enter the study.
Exposed Set (ES)	All participants with at least 1 dose of any of the 2 study interventions documented. Analysis per group is based on the administered intervention.
Per Protocol Set (PPS)	
All eligible participants from the ES who meet all the following requirements:
 
 who received the study interventions according to their random assignment and the expected study intervention administration schedule (see Table 3 and Table 4), and without intercurrent conditions* that may interfere with immunogenicity and without prohibited concomitant medication/vaccination. . for anti-poliovirus types 1, 2 and 3 analyses at 1 month post Dose 3 of IPV, participants should have pre- and post-vaccination immunogenicity results for at least 1 antigen and should have complied with interval between IPV Dose 3 and the post IPV Dose 3 blood sample. for anti-RV IgA analyses at 1 month post Dose 2 of Rotarix PCV-free, participants should have pre- and post-vaccination immunogenicity results and should have complied with the interval between Rotarix Dose 2 and the post Rotarix PCV-free Dose 2 blood sample.

* immunosuppressive or immunodeficient conditions identified before Visit 7.

9.2.1. Criteria for elimination from analysis

If a participant meets one of the criteria mentioned in [Table 15](#) or ones listed in the Section [7.1.1](#), they may be eliminated from PPS.

9.3. Statistical analyses

The statistical analysis will be detailed in the statistical analysis plan (SAP), which will be developed and finalized prior to the first subject first visit (FSFV). This section is a summary of the planned main statistical analyses of the primary/secondary immunogenicity, reactogenicity and safety endpoints and the descriptive analyses of demography summaries.

The analysis of immunogenicity will be primarily based on the PPS. The analysis of safety will be based on the ES.

9.3.1. Primary endpoint analysis

The primary endpoints are described in Section [3](#). The Mittinen and Nurminen 95% CI for the group difference (Co-administration group minus Staggered group) in the seroconversion rate of anti-poliovirus types 1, 2 and 3 antibodies at Visit 7 will be computed. Refer to Section [9.1](#) for details on how this will be used to conclude whether the primary objective is reached.

9.3.2. Secondary immunogenicity endpoints analysis

The secondary endpoints are described in Section [3](#).

Anti-RV IgA Ab seroconversion rate and the percentage of participants with anti-RV IgA antibody concentration ≥ 90 U/mL at 1 month post Dose 2 of *Rotarix*; and the percentage of participants with poliovirus types 1, 2 and 3 neutralizing antibody titers $\geq 1:8$ and $\geq 1:64$ at 1 month post Dose 3 of IPV will be summarized by group with 95% CI.

For all antigens and timepoints as applicable, GMT/GMC will be computed with 95% CI. The 95% CI will assume that log transformed titer/concentration is normally distributed. For the purpose of GMT/GMC computation, titer/concentration below the assay cut-off will be assigned half of the cut-off.

For each of the anti-poliovirus types 1, 2 and 3, group GMT ratio at Visit 7 will be computed with 95% CI using an analysis of variance (ANOVA) model on log transformed titer in order to characterize the impact of co-administration on the IPV response. The group GMC ratio, the difference in seroconversion rates and the difference in the percentage of participants with concentration ≥ 90 U/mL will not be computed for anti-RV IgA antibody because a difference may be either attributed to co-administration of *Rotarix* PCV-free with IPV, or to the difference in administration schedule for *Rotarix* PCV-free (Month 0.5 and Month 1.5 in the Co-administration group, and Day 1 and Month 1 in the Staggered group).

Reverse cumulative curve will be provided for each antigen and timepoint as applicable.

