6.3.3. Intervention allocation to the participant

The system's randomization algorithm will use a minimization procedure accounting for center and the study as a whole as minimization factors. Minimization factors will have equal weight in the minimization algorithm.

Once a participant identification number is allocated, the randomization system will determine study group and will provide the study intervention number to be used for the first dose. The study intervention number(s) to be used for subsequent dosing will be provided by the same automated Internet-based system (Source Data Base for Internet Randomization [SBIR]).

When SBIR is not available, please refer to the SBIR user guide or Pharmacy Manual for specific instructions.

Refer to the Pharmacy Manual for additional information about the study intervention number allocation.

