Study intervention Assignment	
Participants will be randomly assigned (1:1) to the 2 study groups (Co-administered and Staggered).
 
The numbering of HRV vaccine supplies will be performed at GSK, using a block scheme randomization in MATerial EXcellence, a program developed by GSK. Entire blocks will be shipped to the study centers/warehouse(s).
 
To allow GSK to take advantage of greater rates of recruitment than anticipated at individual centers in this multicenter study and to thus reduce the overall study recruitment period, an over-randomization of supplies will be prepared.
		
Interim Analysis	
No interim analysis is planned.
 
All analyses will be conducted on final data.
 
The final analysis will include all data up to one month after the third dose of IPV. These analyses will include the final analysis of immunogenicity and the final analysis of solicited and unsolicited symptoms and SAEs from the first dose up to Visit 7.
		

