4. STATISTICAL ANALYSES

4.1. General Considerations

4.1.1. Immunogenicity

- GMC/GMT concentrations/titers below the assay cut-off will be given an arbitrary value of half the assay cut-off for the purpose of GMC/GMT calculation.
- The GMC/GMT calculations will be performed by taking the anti-log of the mean of the log concentration/titer transformations.
- Seroconversion rate for IPV neutralizing Ab is defined as percentage of participants with
 - Titer $\geq 1:8$ at 1 month after 3 dose primary schedule of IPV in participants who are seronegative before Dose 1 (titer $< 1:8$ pre-vaccination).
 - ≥ 4 -fold increase in titer 1 month after 3 dose primary vaccination schedule in participants who are seropositive before Dose 1 (titer $\geq 1:8$ pre-vaccination) after adjusting for maternal antibody decay assuming a half-life of 28 days.
- Seroconversion rate for *Rotarix* is defined as the percentage of participants who were initially seronegative (i.e., prior the first dose of *Rotarix*) and developed anti-RV IgA Ab concentration ≥ 20 U/mL 1 month post Dose 2.
- For a given participant and a given immunogenicity measurement time point, missing or non-evaluable measurements will not be replaced.

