4.2.2. Between groups assessment

The asymptotic standardized 95% CI for the difference in seroconversion rate for IPV at Visit 7 between Co-administration group minus staggered group will be computed using the method of Miettinen and Nurminen [[Miettinen](#), 1985]

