4.2.3. Sensitivity analyses

If more than 5% of the ES participants with immunogenicity results after study intervention are excluded from the PPS, the confirmatory analysis will be repeated on the ES.

Within groups assessment for the PPS will be repeated by sex and study sites.

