4.3.2. Between group assessment

- The asymptotic standardize 95% CI for the difference in the percentage of participants with anti-poliovirus types 1, 2 and 3 neutralizing Ab titers $\geq 1:8$ and $\geq 1:64$ at Visit 7 between Co-administration group minus staggered group will be computed.
- The 95% CI for the ratio of anti-poliovirus type 1, 2 and 3 Ab GMTs at Visit 7 between Co-administration group over staggered group will be computed.

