4.8. Changes to Protocol Defined Analyses

There were no changes or deviations to the originally planned statistical analysis specified in the protocol amendment 1 (Dated: 25 October 2023).

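### Allocation is minimised on centre, but the GMT-ratio ANOVA reads as group-only and no between-group immunogenicity comparison is stated to use centre

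*Protocol*

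**What the plan says.** **Allocation.** Protocol 6.3.3 says the system "will use a minimization procedure accounting for center and the study as a whole as minimization factors", with equal weights. SAP 1.2 confirms that there are several sites, justifying the surplus supplies by faster recruitment "than anticipated at individual centers in this multicenter study".

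**GMT ratio.** Protocol 9.3.2 states that the "group GMT ratio at Visit 7 will be computed with 95% CI using an analysis of variance (ANOVA) model on log transformed titer". It gives the purpose (to describe how co-administration affects the IPV response) but no factors or covariates. SAP 4.3.2 promises only "The 95% CI for the ratio of anti-poliovirus type 1, 2 and 3 Ab GMTs at Visit 7" and names no model. SAP 4.1.1 gives the arithmetic for a GMT: "The GMC/GMT calculations will be performed by taking the anti-log of the mean of the log concentration/titer transformations". SAP 4.8 then states: "There were no changes or deviations to the originally planned statistical analysis specified in the protocol amendment 1".

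**Other between-group comparisons.** SAP 4.2.2 plans "The asymptotic standardized 95% CI for the difference in seroconversion rate for IPV at Visit 7 between Co-administration group minus staggered group" by the Miettinen-Nurminen method and names no strata. Neither do the SAP 4.3.2 differences in the percentages reaching 1:8 and 1:64.

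**Where site appears.** In the immunogenicity plan it enters once, in SAP 4.2.3: "Within groups assessment for the PPS will be repeated by sex and study sites". Otherwise it appears in disposition and baseline tables (SAP 6.1.1 and 6.1.2).

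**The concern.** An analysis would normally reflect the factors used to allocate. Balancing on centre makes the two groups alike in centre mix, so centre differences contribute little to the error of the group contrast. A group-only ANOVA still counts those differences as residual noise. Its standard error is then larger than the design warrants.

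The by-site repeats in SAP 4.2.3 do not recover this, because they summarise each group separately and compare nothing.

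At stake is the precision of the ratio that the plan uses to describe the effect of co-administration on titres. There is also a gap in pre-specification: Protocol 9.3 leaves the detail to the SAP, the SAP does not list the terms, and the trial is open-label.

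**Working it through.** **1. The plan's own figures.** Protocol 9.7 and SAP 5 assume 160 evaluable per group, rates of 96.23%, 93.83% and 97.60%, no true difference, a margin of -10% and one-sided alpha of 0.025. Exact enumeration of the unstratified Miettinen-Nurminen test gives:

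| Type | Stated power | Recomputed |
|---|---|---|
| Polio 1 | 98.2% | 98.6% |
| Polio 2 | 92.5% | 93.8% |
| Polio 3 | 99.7% | 99.8% |
| Overall | 90.4% | 92.1% |

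The stated overall figure follows from its parts: 1 - (0.018 + 0.075 + 0.003) = 90.4%. Also 160 / 0.8 = 200 per group. The stated power is therefore reproduced to within 2 points by an unstratified two-group comparison with no centre term.

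**2. Gain from adding centre, by formula.** Let *s* be the share of log-titre variance between centres. The documents do not give it, so it is assumed. With groups balanced within centre, the interval narrows by 1 - √(1 - *s*):

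- *s* = 0: 0%
- *s* = 0.02: 1 - √0.98 = 1.0%
- *s* = 0.05: 1 - √0.95 = 2.5%
- *s* = 0.10: 1 - √0.90 = 5.1%

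**3. Gain by simulation.** Assumptions: 320 evaluable infants; minimisation on centre and whole study with equal weights and a 10% random element; 4 or 8 equal centres; no group effect; 4000 runs per scenario.

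| *s* | Narrowing, 4 / 8 centres | Group-only coverage, 4 / 8 centres | Coverage in theory |
|---|---|---|---|
| 0 | 0.0 / 0.0% | 94.5 / 94.8% | 95.0% |
| 0.02 | 0.8 / 0.9% | 95.5 / 94.9% | 95.2% |
| 0.05 | 1.9 / 2.2% | 95.7 / 95.3% | 95.6% |
| 0.10 | 3.8 / 4.4% | 95.6 / 95.9% | 96.1% |

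With centre in the model, coverage was 94.6 to 95.5%. The gain is below the formula because K centres realise on average only (K - 1)/K of the nominal between-centre variance. At *s* = 0.10 and K = 4, 1 - √(0.9 / (0.9 + 0.1 × 3/4)) = 3.9%.

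A second simulation with exact balance in 4 equal centres gave group-only standard errors 1.008, 1.019, 1.040 and 1.089 times the centre-adjusted ones at *s* = 0.02, 0.05, 0.10 and 0.20. Group-only coverage reached 96.5% at *s* = 0.20.

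**4. What this means on the ratio scale.** The titre SD is not given; assume 0.5 log10. The half-width is 1.967 × 0.5 × √(2/160) = 0.110 log10, so the limits are the ratio divided and multiplied by 10^0.110 = 1.288.

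- By formula the factor becomes 1.285, 1.280 or 1.271 at *s* = 0.02, 0.05 or 0.10.
- With the simulated gains of 3.8 and 4.4% at *s* = 0.10 it becomes 10^(0.110 × 0.962) = 1.276 and 10^(0.110 × 0.956) = 1.274.
- By formula at *s* = 0.10, it goes from 1.225 to 1.212 for an SD of 0.4, and from 1.425 to 1.400 for an SD of 0.7.

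**5. Primary endpoint.** The unstratified test was simulated for Polio 2 (mean rate 93.83%, four equal centres assumed):

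| Centre rates | Type I error at -10% | Power at 0 |
|---|---|---|
| Equal | 2.3% | 93.8% |
| About 90-97% | 2.4% | 93.9% |
| About 86-99% | 2.3% | 94.3% |

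Expected non-responders per group are 160 × 3.77% = 6.0, 160 × 6.17% = 9.9 and 160 × 2.40% = 3.8. That is too few to make a centre-stratified interval a good confirmatory choice.

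**The case against.** The strongest reply is that the documents never exclude centre. The ANOVA terms are simply not listed, Protocol 9.3 calls itself a summary, and the SAP 4.1.1 formula describes a GMT within a group, not the ratio model. That stands, and it is why the point is put as *reads as group-only* and *not stated to be used*. But the SAP was the place to add terms, and it added none.

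Second, nothing formal depends on the ratio. It is descriptive and has no margin or success rule. This also stands, and it sets the low priority.

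Third, the size rests on assumptions and may be zero. One country, one IPV product, a narrow age range and a designated laboratory all argue for a small centre share. That is fair, and the range above starts at zero for that reason.

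Fourth, a group-only ANOVA returns exactly the ratio of the GMTs displayed by group, whereas a centre-adjusted ratio may not. This is a good reason to report both, not a reason to leave centre out.

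**Conclusion.** The concern holds as a low-priority improvement. Centre is used to allocate, the GMT-ratio model reads as group-only, and no between-group immunogenicity comparison is stated to use centre. The consequence is an interval that is at worst conservative, with coverage of about 96% at a 10% centre share.

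At that share the multiplying factor falls from 1.29 to about 1.27 or 1.28, assuming an SD of 0.5 log10 and 160 per group. At a zero share nothing is lost. The number and size of centres, the centre share and the titre SD are all assumed. Type I error, the primary conclusion and the stated power are not affected.

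**What to change.** In SAP 4.3.2, state the GMT-ratio model as an ANOVA on log titre with group and centre as fixed factors. Fix a pooling rule for small centres in advance, for example pooling those with fewer than 10 participants in the per-protocol set. Report the group-only ratio alongside. If the sponsor prefers group-only, say so and give the reason.

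Keep the unstratified Miettinen-Nurminen interval as the confirmatory analysis. A centre-stratified version is optional and should be a sensitivity analysis only.

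One caution: raw pre-vaccination titre is not planned as a covariate and should not be added when this model is written out. Protocol 8.1.3 has that sample drawn at Visit 1 in the Staggered group and at Visit 2 in the Co-administration group, so its raw values are not comparable between groups.

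The cost is one or two sentences and one model term, with no new data and no change to the confirmatory test.
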